Current practice guidelines from the American Association of Critical-Care Nurses (AACN) call for verification of distal tube placement every 4 hours using multiple methods [2], yet there are no valid methods available to perform this assessment. Existing tube verification methods such as pH measure, capnography, observation of gastric aspirate, and signs of respiratory distress have lacked validity [3-5]. The tradition-based method of auscultation has insufficient sensitivity and specificity to identify FT placement and should no longer be used [5-7]. Although these verification methods pose little risk for patient harm, they are resource intensive (financial and clinician time). Clinicians are encouraged to question whether current practices are based on research evidence or if they are tradition-based [8]. Tradition-based practices should then be assessed to determine if they should be de-implemented (stopped), changed, or replaced [8].

A gap in the literature is whether FTs migrate over time. Forward migration is known to occur due to normal gastric motility [9] and has been documented numerous times by radiographic confirmation. In fact, clinicians often rely on this naturally occurring forward migration to assist with FT placement into the small bowel in instances where gastric placement has been confirmed and small bowel FT placement remains elusive. Reverse migration could potentially pose greater risk to the patient if the FT migrated from the small bowel into the stomach [1]. In this instance, formula and medications may not be well absorbed or tolerated, leaving the patient deficient in nutrition and necessary medications and putting them at risk for aspiration should the volume of gastric contents become too great. Additionally, reverse migration from the stomach to the esophagus may place the patient at an even higher risk of aspirating formula and/or medications into the pulmonary system. Pulmonary aspiration has led to pneumonia and has also resulted in death [11].

The proposed study will use an electromagnetic placement device (EMPD), Cortrak* 2 Enteral Access System (EAS™), Avanos Medical, to verify FT position on a daily basis to assess for migration. The EMPD provides real-time FT placement data. A sensor located on the distal end of the FT guidewire communicates with a receiver unit which sits on the patient's abdomen. Three visual insertion tracings with varying views (anterior, lateral, and depth/cross-section) can be saved and printed for comparison. (See Figure 1)

Two previous studies have been completed with similar methodology. A pilot study of 50 subjects was performed using the original Cortrak* (2 insertion views) and found only minimal forward migration [9]. No reverse migration was reported in the Powers study.

DrIFT 2 STUDY: DISPLACEMENT IN FEEDING TUBES

A pilot study of 20 patients with 62 feeding tube assessment identified 8 migration events (5 retrograde and 3 forward), these events only occurred within the small bowel [10]. Based on this data, a recommendation could be made that there is no need to check feeding tube placement routinely q4hours. However, due to the small sample size, additional research is needed to confirm this finding. It is also unknown if there may be more migration with positioning changes, for example, up in the chair or prone position.

The proposed study will use an electromagnetic placement device (EMPD), Cortrak* 2 Enteral Access System (EAST™), Avanos Medical, to verify FT position on a daily basis to assess for migration. The proposed study will take place in critical care units at Parkview Health. The primary aim will be to determine if replication of the pilot study results in similar findings. We will also explore other factors that may be associated with FT migration, such as patient mobility (ambulation or sitting at bedside or prone position) and transporting out of the critical care unit for diagnostic procedures. We anticipate that results from this study will provide a better understanding of FT position and migration over time and ultimately influence recommendations for practice for frequency of routine FT verification. Standard of care for assessing feeding tube placement location every 4 hours will remain in place. The study will add an additional assessment for feeding tube location daily. This study will expand on the findings from the initial pilot study with a larger sample size.

3 Primary Objective

Determine if small bore FTs migrate over time in critically ill adults receiving usual care.

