3.1 Secondary Objectives

1. Identify factors associated such as mobility and position changes that may affect feeding tube migration.
2. Findings may inform recommendations for clinical practice regarding the frequency for FT placement verification.
3. Validate current dual verification process for feeding tube confirmation.

4. Study Population

The sample recruited for this study will include adult patients in critical care with small bore feeding tubes (FT) in acute and critical care. All participants must be able to understand and fluently speak English.

Investigators will review patient census and data from cortrak to identify new small bore feeding tube insertions in adult patients on the designated study units and will assess eligibility criteria. We are aiming for a sample of 120 feeding tubes.

Parkview Health, Fort Wayne, IN

- Surgical trauma ICU (STICU) and Medical ICU (MICU)

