4.2 Exclusion Criteria

- <18 years old
- Identified as “Doe”
- Unable to speak or understand English language
- Pregnancy
- Prisoners
- FT anticipated to be removed within 24 hours
- Contraindications to placing a mark on the abdomen for top foot of receiver unit (large dressings, open abdomen, halo vest, etc.)
- Original guidewire unavailable

5. Vulnerable Populations

No vulnerable populations will be targeted for enrollment but may be included except for pregnant patients and prisoners, which will be excluded.

6. Study Design

This study will use a longitudinal, repeated measures design replication study from previous pilot study.

An investigator will perform recruitment and data collection. Additional data collectors will be used as needed to ensure that data collection is performed daily, including weekends. Since this practice was safely completed in a pilot study as well as a previous study and is currently standard practice to assess tube location as needed, a waiver of written informed consent is being requested. Explanation will be provided to patients/family that we are evaluating the tube daily to assess any movement of the feeding tube.

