6.3 Data Collection

Data collection will be an ongoing process and take place every 24 hours (+/- 6 hours) following enrollment. A 6-hour window before or after the designated 24-hour data collection period was allowed for feasibility of data collection. Data collection will continue daily for the duration of the feeding tube or until Day 5. If the patient is transferred off the study unit to a medical or surgical unit at PRMC, data collection will continue. Data collection will cease at 5 days or when the feeding tube is removed.

DrIFT 2 STUDY: DISPLACEMENT IN FEEDING TUBES

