The primary risk for this study is microbial contamination with insertion of the stylet [12] – to mitigate this risk, the stylet will be cleaned with alcohol before every insertion.

Loss of confidentiality is always a risk, participation in the study will remain confidential. All demographics and data collected for research purposes will remain confidential. Only the assigned unique study number will be used. Measures will be in place to mitigate the risk for loss of confidentiality, data will be stored on a password protected Parkview computer. Any paper data collection forms will be kept in a locked drawer in a locked investigators office.

11.2 Benefits to Participants:

There may not be any direct benefits to individual participants in this study. There may be benefits for future patients with small bore feeding tubes since findings from this study have the potential to influence frequency of feeding tube verification. Knowledge obtained from this study may be beneficial not only for the study sites, but internationally.

12. Safety Monitoring, Interim Analysis, and Stopping Rules

Our study contains no more than minimal risk to the participants.

13. Conflict of Interest

There is no conflict of interest with any of the researchers involved with this study.

14. Publication and Presentation Plans

DrIFT 2 STUDY: DISPLACEMENT IN FEEDING TUBES

Findings from this study will be presented by poster or podium at a national meeting, such as the National Teaching Institute (NTI) of the American Association of Critical-Care Nurses (AACN). Findings will also be disseminated in a publication, such as American Journal of Critical Care. Also, as per OH policy, we will plan to present the findings from this study at a Center for Nursing Research meeting.

15. References

1. Metheny, N.A., B.J. Stewart, and S.A. McClave, *Relationship between feeding tube site and respiratory outcomes*. JPEN J Parenter Enteral Nutr, 2011. **35**(3): p. 346-55.
2. Metheny, N., *Initial and Ongoing Verification of Feeding Tube Placement in Adults*. Critical Care Nurse, 2016. **36**(2): p. e8-e13.
3. Bourgault, A.M., et al., *Methods used by critical care nurses to verify feeding tube placement in clinical practice*. Critical Care Nurse, 2015. **35**(1): p. e1-e7.
4. Metheny, N.A., B.J. Stewart, and A.C. Mills, *Blind insertion of feeding tubes in intensive care units: a national survey*. Am J Crit Care, 2012. **21**(5): p. 352-60.

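### Secondary objective 2: a low rate of zone change on daily tracings would be ambiguous, because 4-hourly checks continue for every tube and the plan does not record what they find or correct

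*Combined protocol and SAP*

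**What the plan says.** **Checking and measurement.** The background text ahead of section 3 keeps routine checking for every tube: "Standard of care for assessing feeding tube placement location every 4 hours will remain in place". To this, "The study will add an additional assessment for feeding tube location daily". Section 6.3 gives the timing: "Data collection will be an ongoing process and take place every 24 hours (+/- 6 hours) following enrollment", and "Data collection will continue daily for the duration of the feeding tube or until Day 5". Section 6 describes one cohort: "This study will use a longitudinal, repeated measures design replication study from previous pilot study". No tubes are assigned to less frequent checking.

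**Intended use.** The background reports 8 migration events in 62 assessments of 20 pilot patients, all within the small bowel. It says these data would support advising that "there is no need to check feeding tube placement routinely q4hours". It gives the small sample as the reason for more research and adds that the effect of position changes is unknown. Section 3.1, item 2 reads: "Findings may inform recommendations for clinical practice regarding the frequency for FT placement verification". Section 11.2 says that "findings from this study have the potential to influence frequency of feeding tube verification".

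**What is recorded.** Section 8.1 lists migration (yes/no), hours to movement, direction and tip zone. It also lists covariates such as observed pulling on the tube, length inserted, the centimetre mark at original insertion, bridle and x-ray. It has no item for the result of a 4-hourly check or for repositioning by staff between tracings. Under section 6.4.1 a tube found pulled back is documented with the cause and then advanced. The section does not say whether this covers tubes that staff find between study tracings.

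**The concern.** Each tracing shows where the tip is now, compared with about a day earlier. What happened in between is seen only if it leaves a net change. Meanwhile the practice whose frequency is in question is running on every tube. If a check finds a displaced tube and staff put it back before the next tracing, the study records no migration. The same holds for a tip that moves and returns unaided.

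The ambiguity runs one way. Many moves seen despite the checks would be informative. Few moves seen could mean that tubes are stable or that the checks are working, and these two readings point in opposite directions on verification frequency. The background already argues from pilot tracings towards dropping routine 4-hourly checks, so a larger study with a low rate would probably be read the same way. Nothing in the plan limits that reading.

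**Working it through.** The plan gives no figure on this point to reproduce. Its sample size statement (120, effect size 0.18) does not enter the argument.

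**1. What the record can distinguish.** Three histories between two tracings:

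| History | Tracing shows | Separate record in section 8.1 |
|---|---|---|
| Tip stays in place | no zone change | none needed |
| Tip moves, a check finds it, staff reposition it | no zone change | none listed |
| Tip moves and returns unaided | no zone change | none listed |

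All three count as no migration. Section 6.4.1 would separate the second from the first only if it covers staff findings between tracings.

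**2. How much correction could hide.** Inputs from the documents: checks every 4 hours and tracings 24 hours apart, so 24/4 = 6 check intervals. Assumptions, not document figures: a move is equally likely in each interval k = 1 to 6; each later check detects and corrects it with probability s; the tracing falls just before the 24-hour check. A move in interval k then faces 6 − k checks before the tracing, so

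share visible = (1/6) × Σ (1 − s)^(6 − k), k = 1 to 6.

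| s | Share visible | True daily rate if 2% is observed |
|---|---|---|
| 0 | 100% | 2.0% |
| 0.1 | 4.686/6 = 78% | 2.6% |
| 0.25 | 3.288/6 = 55% | 3.6% |
| 0.5 | 1.969/6 = 33% | 6.1% |
| 1 | 1/6 = 17% | 12% |

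The last column is 0.02 divided by the share visible; the 2% is illustrative. If the 6-hour window applies to fixed daily times, consecutive tracings may be 12 to 36 hours apart (3 to 9 intervals). At s = 1 the share visible is then 4/12 = 33% down to 4/36 = 11%.

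**3. Moves that reverse unaided.** With random onset, a displacement lasting D hours is present at a once-daily tracing with probability D/24. For assumed durations of 4, 8 and 12 hours this is 17%, 33% and 50%. The documents give no durations and no frequency of such moves.

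**4. A larger sample does not settle it.** The pilot rate was 8/62 = 12.9% per assessment (exact 95% interval 5.7% to 23.9%, treating assessments as independent). With zero events, the one-sided 95% upper bound is 1 − 0.05^(1/n): 4.7% for n = 62 and 0.5% for n = 600 (at most 120 tubes × 5 days). That is a tighter bound on net displacement under 4-hourly checks. It does not say which history in step 1 produced the result.

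**The case against.** **The checks may correct very little.** This is the strongest objection. The background says that no valid method exists for the 4-hourly assessment and that auscultation lacks sensitivity and specificity. If so, s is near 0 and nearly all moves stay visible (78% even at s = 0.1). No section says that checks lead to correction between tracings. This stands as a reason to expect small masking by correction. But the plan does not use the argument to support its inference, does not measure s, and the argument does not cover moves that reverse unaided.

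**The pilot argument is about location as well as count.** The events were confined to the small bowel, and the new study records tip zone. That is fair, and the 12.9% pilot rate was not especially low. Yet zone is read from the same daily tracing. A tip that reached the stomach and was re-advanced before the next tracing would be missing from the zone record too.

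**The aim is hedged.** Objective 2 says only that findings may inform practice, no test is attached to it, and section 8.1 looks ahead to a larger study. This also stands. A reader might infer that the study has nothing to say about verification frequency, or that the plan promises to prove the checks unnecessary. The documents support neither.

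**Some capture already exists.** Section 6.4.1 records pulled-back tubes and draws on nurses and the EMR; section 8.1 collects observed pulling and length inserted. These help, but none records what a check found or whether staff repositioned the tube.

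**Conclusion.** The point holds as a limit on one secondary use of the data. The primary objective asks about migration in patients under usual care, and the design measures that. For secondary objective 2, a low rate of zone change is ambiguous because corrected and self-reversing moves are counted as no migration and nothing listed would reveal them.

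The size is unknown. The range of 100% down to 17% visible rests on an assumed s, even timing of moves and 24-hour gaps. A reader might infer from it that a substantial fixed share of moves will be missed. The documents do not support that: they give no correction rate and no duration of displacement, and their own view of the check methods points to the small end. What is established is that the plan, as listed, could not tell which end applies. It should be amended, because a small addition to the data would change what can be concluded.

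**What to change.** 1. **Record the checks.** Add to the EMR and nurse abstraction in section 8.1, for each tracing interval: whether any 4-hourly check flagged displacement, and whether the tube was repositioned, with the time.
2. **Clarify section 6.4.1.** State whether the pulled-back record covers staff findings between tracings.
3. **Define the counting rule.** Say in section 8 whether repositioning between tracings counts as a migration event or is reported separately. Tabulate it against zone changes found on tracing. If the checks find almost nothing, that is direct evidence for the view in the background text.
4. **Limit the wording.** Express secondary objective 2 and the planned conclusion as net displacement and tip zone at about 24-hour intervals under continuing 4-hourly checks, and state that this alone does not show the effect of checking less often.

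The cost is a few extra fields per interval from sources already in use, slight abstraction time and a more modest claim. Moves that reverse unaided and are not charted would still be missed, which the wording in item 4 covers. No change to clinical checking is proposed.

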3.1 Secondary Objectives

1. Identify factors associated such as mobility and position changes that may affect feeding tube migration.
2. Findings may inform recommendations for clinical practice regarding the frequency for FT placement verification.
3. Validate current dual verification process for feeding tube confirmation.

4. Study Population

The sample recruited for this study will include adult patients in critical care with small bore feeding tubes (FT) in acute and critical care. All participants must be able to understand and fluently speak English.

Investigators will review patient census and data from cortrak to identify new small bore feeding tube insertions in adult patients on the designated study units and will assess eligibility criteria. We are aiming for a sample of 120 feeding tubes.

Parkview Health, Fort Wayne, IN

- Surgical trauma ICU (STICU) and Medical ICU (MICU)

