4.1 Inclusion Criteria

- Adult ≥ 18 years old
- Critical care patients with small bore feeding tube inserted within last 24-48 hours
- Initial Cortrak insertion tracings: all 3 views available
- Cortrak guidewire available (these are typically saved in a plastic bag in the patient room following FT insertion).

DrIFT 2 STUDY: DISPLACEMENT IN FEEDING TUBES

Ethic/racial diversity, age, or sex are not anticipated to play a role, so our recruitment will not focus on a diverse sample.

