6.4 Methods: PI or Sub-I

- Investigators will discuss the study with the patient or designated family member so they understand the process steps.
- Label original Cortrak* guidewire with tape ("DrIFT Study") near orange Cortrak connector port.
- Obtain insertion tracings from original feeding tube insertion.

6.4.1 Subsequent Insertions:

- Verify that original guidewire is available (see tag on proximal end).
- Position patient supine, HOB elevated 30 degrees. If unable to place supine, document position
- Connect Cortrak to guidewire. Wipe guidewire with alcohol before insertion
- Position Cortrak receiver unit on abdomen. At the time of the first data collection, a surgical marker will be used to indicate location for placement of the top foot of the receiver unit (see image attached) on the patient's abdomen. Subsequent data collection will align the top foot of receiver unit with the mark on the patient's abdomen.
- Flush FT with 30ml water per institutional protocol.
- Insert guidewire into FT and obtain Cortrak insertion tracing to determine position of distal tip of feeding tube.
- Print 3 insertion tracings (anterior, lateral, depth/cross section). Write unique identifier on the back of each tracing printout. Do not write any other information on the insertion tracing.
- Remove guidewire, wipe with alcohol and leave in bag at the bedside.
- If tubes are found to be pulled back, this will be documented along with precipitating factors. Tube will then be advanced and will continue data collection noting the change in position on data collection form.

Other study data will be entered onto a hard copy, printed data collection form and stored temporarily in the locked office of the site Sub-II. Study data will be obtained from patient observation, discussion with the nurse, and the EMR.

7. Study Duration/ Study Timeline

The proposed study will take place over a 10 month period after IRB approval. Dissemination of study findings will take place via poster or podium presentation at an appropriate conference and also published in a peer-reviewed journal.

Study Timeline

	Dec	Jan 2024	Feb	March	April	May	June	July	Aug	Sept
IRB Submission										
Recruit Participants										
Perform /Data Collection										

DrIFT 2 STUDY: DISPLACEMENT IN FEEDING TUBES

Data Analysis										
Dissemination by poster/manuscript										

8. Statistical Analysis Plan

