8.1 Data Analysis

Data analysis will be performed using the appropriate statistical analysis software, such as IBM SPSS, SAS, etc. Descriptive statistics will be used to discuss demographics of the participants. An alpha level of 0.05 will be used to determine statistical significance for all analyses.

Outcome variable:

- Feeding tube migration (yes/no).
 - Number of hours from insertion to tube movement
 - Forward migration/backward migration
 - Zone of the FT distal tip (figure 1)

Figure 1. FT Placement/Migration Zones

Independent variables: These variables that possibly have an association with FT migration will be collected and will help to inform the design of a larger R01 study.

- Patient bedside observation
 - Date/time of data collection
 - Date/time of feeding tube insertion
 - Documentation of dual verification at initial insertion

DrIFT 2 STUDY: DISPLACEMENT IN FEEDING TUBES

- Length of feeding tube
 - Diameter of feeding tube 10 FR, 8 FR, other
 - Rate of formula ____ ml/hr
 - Bolus via FT yes/no, volume ____ ml/hr, frequency: every ____ hours
 - Cortrak device serial number
 - Length of FT inserted ____ cm
 - Mark present on abdomen for receiver unit placement? If not, apply mark using surgical marker and indicated date/time.
 - bridle present (yes/no)
 - Patient position supine/HOB elevated 30 degrees (yes/no). If no, identify position.
- EMR
 - Medical record number on enrollment form that is linked to unique study number. Do not write MRN on data collection form.
 - Was dual verification performed (yes/no).
 - Was x-ray obtained for verification (yes/no)
 - CM mark at nares at time of original insertion
 - Patient demographics
 - Sex
 - Age
 - Weight
 - Diagnosis
 - Height in cm
 - Factors that may impact motility: abdominal compartment syndrome, gastric ileus, abdominal distension, ascites or hepatic enlargement
 - Metoclopramide (yes/no)
 - Erythromycin (yes/no)
 - Vasopressors: identify by name.
 - Vomiting/retching (yes/no)
 - Excessive coughing (yes/no) ask nurse
 - Observed pulling on FT (yes/no)
 - Ambulation (yes/no)
 - Sitting on side of bed or up in chair (yes/no)
 - Prone position
 - Transfer off unit for diagnostic test/surgery or procedure (yes/no) name of test_____ date/time_____
 - Endotracheal tube removed (yes/no) date/time_____
 - Endotracheal tube replaced (yes/no) date/time_____

9. Informed Consent Process

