The primary risk for this study is microbial contamination with insertion of the stylet [12] – to mitigate this risk, the stylet will be cleaned with alcohol before every insertion. This study presents low risk level to the patients and a waiver of written informed consent is being requested.

10. Privacy and Confidentiality

Each participant will be assigned a unique study number, which will be known only to the site specific Sub-I and PI. This study number will be used to identify all data collected for the purpose of research. Data collection will be performed on printed forms by the PI or Sub-I. Data collection forms will contain only the participant's unique study number and will be de-

DrIFT 2 STUDY: DISPLACEMENT IN FEEDING TUBES

identified. Data collection forms will be stored temporarily during the data collection period in a locked office of the Sub-I. Data will then be entered into a spreadsheet on a password protected Parkview computer. Data will be maintained for a minimum of five years after the completion of the study. Only the investigators will have access to the study data.

Cortrak insertion tracings will be scanned for electronic storage. De-identified insertion tracings from each site, labeled with the file name containing unique study numbers only, will be sent to the other study site for confirmation of FT placement. Having two Sub-Is identify FT placement will increase fidelity of the study. If both Sub-Is are not in agreement regarding the zone of the distal FT tip, the other investigators on the study team (PI and Sub-I) will assess and come to consensus. Transmission of scanned insertion tracings will be sent by institutional email using the confidential setting.

An electronic file linking patient identifiers (human subjects' name, MRN, and study site) and unique study number will be kept in a file on the password protected computer of the PI. Only the principal investigator will have access to this file. The participant identification number will be kept separate from the data collected.

11. Risk/Benefit

11.1 Risk to Participants:

There are minimal risks associated with this study. Insertion of the FT guidewire and verification of FT placement using Cortrak is a standard procedure that can be performed any time that the clinician is uncertain about the position of a FT. The risk to the patient are primarily during the initial insertion, this study will only enroll patients who have the feeding tube currently in place.

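### Secondary objective 3 (validating dual verification) cannot be answered from the listed variables and analyses: no item explicitly asks for the location found, and no comparator or agreement analysis is named

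*Combined protocol and SAP*

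**What the plan says.** Section 3.1 gives the third secondary objective as "Validate current dual verification process for feeding tube confirmation".

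Three items in Section 8.1 bear on it:
- at the bedside, "Documentation of dual verification at initial insertion", with no response format stated;
- from the EMR, "Was dual verification performed (yes/no";
- from the EMR, "Was x-ray obtained for verification (yes/no".

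All three stand under the independent variables, which Section 8.1 introduces as factors that may be related to migration. The one tip-location variable, "Zone of the FT distal tip (figure 1", stands under the migration outcome.

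The study also secures tracings from the insertion itself. Section 4.1 requires "Initial Cortrak insertion tracings: all 3 views available", and Section 6.4 instructs staff to "Obtain insertion tracings from original feeding tube insertion". Section 10 has two Sub-Is identify placement from the tracings, with a consensus step "If both Sub-Is are not in agreement regarding the zone of the distal FT tip".

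Sections 8 and 8.1 name a mixed effects model (in the sample-size text), chi-square tests, t-tests or Wilcoxon tests, a Kaplan-Meier method for repeated events, and descriptive statistics. The group comparisons are by migration status.

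**The concern.** To validate a confirmation process, one needs the result that the process gave, a reference result for the same tube at the same time, and a stated comparison of the two. The listed items record whether steps were taken. They do not clearly record what was found.

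The study could then finish with a percentage of tubes that had dual verification and a percentage that had an x-ray, and no planned way to say whether the confirmed location agreed with anything. The practical risk is that a high rate of performing dual verification is reported under an objective worded as validation, and is read as evidence that the process is accurate.

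**Working it through.** The plan gives no figure for objective 3 to reproduce. Its only sample-size statement (Sections 6.1 and 8: 120, effect size 0.18, 80% power, alpha 0.05) concerns migration and is not used here. The check sets what validation needs against what is listed.

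**1. The quantity needed.** For tube i, let V_i be the location documented by the verifiers at insertion and R_i the reference location at insertion. Then

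agreement = (number of tubes with V_i = R_i) / (number of tubes with both V_i and R_i recorded).

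**2. Is V_i listed?**

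| Item in Section 8.1 | Stated format | Location explicitly requested? |
|---|---|---|
| Documentation of dual verification (bedside) | none stated | not stated |
| Dual verification performed (EMR) | yes/no | no |
| X-ray obtained (EMR) | yes/no | no |

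Two items cannot hold a location. The third might, but the list does not ask for it.

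**3. Is R_i listed?** No comparator is named. There are three candidates.
- X-ray: only whether one was obtained is listed, not the tip location reported.
- Study-read zone of the insertion tracing: available (Sections 4.1, 6.4, 8.1 and 10), but not given this role.
- Zone from the daily checks: these are timed from enrolment (Section 6.3), and a tube may already be up to 48 hours old at enrolment (Section 4.1). A difference from the location at insertion could be migration, which is the primary question, and not a verification error.

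**4. Is the comparison planned?** Five analyses are named: mixed effects model, chi-square, t-test or Wilcoxon, repeated-events Kaplan-Meier, and descriptive statistics. The first four concern migration or compare patients by migration status; the fifth describes participants. None of the five compares two location readings.

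**5. What the yes/no items can give.** They give the number of tubes verified, the number x-rayed, and the cross-table of the two. The numerator in step 1 appears nowhere in that table. The same counts are compatible with any share of correct confirmations, from none to all.

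**6. What the added fields could give (illustration only).** The documents state neither the share of tubes with an x-ray nor an expected agreement, so both are assumed here. The exact 95% limits for k agreements in n tubes are the 0.025 quantile of Beta(k, n−k+1) and the 0.975 quantile of Beta(k+1, n−k).

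| Tubes with both readings | Agreement 90% | Agreement 95% |
|---|---|---|
| 120 (all) | 108/120: 83.2% to 94.7% | 114/120: 89.4% to 98.1% |
| 60 (half) | 54/60: 79.5% to 96.2% | 57/60: 86.1% to 99.0% |

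Even with half the tubes, the estimate would be informative.

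**The case against.** The strongest reply is that the material is largely there. Insertion tracings in three views are required, two Sub-Is read the zone with consensus on disagreement, and the bedside documentation item is kept separate from the EMR yes/no item, so it may capture more than occurrence. The EMR is already a data source (Section 6.4), and a file links study numbers to medical records (Section 10), so recorded results could be retrieved later. Section 8 also leaves room for further analyses.

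Much of this stands, and it rules out several stronger readings that a reader might infer.
- *That the protocol never defines dual verification.* The text available for review does not include the opening part of the protocol or the printed data collection form, so this cannot be claimed.
- *That all three items definitely omit the location.* Only the two yes/no items do; the third is undetermined.
- *That the study holds no location at insertion.* A study-read zone is available from the insertion tracings.
- *That the information is lost for good.* Anything recorded in the EMR could still be abstracted, subject to approvals.

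The reply does not close the gap. The Sub-I reading is a quality step for the study's own zone; it is not the current clinical process that objective 3 names. Without the verifiers' result there is nothing to set against that zone. An open allowance for further analyses names neither a comparator nor a measure. Even if the form does hold a location, the comparator and the comparison remain unstated.

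**Conclusion.** The point holds in this form: from the variables and analyses listed in the text available, objective 3 cannot be answered. Two of the three related items are yes/no and one has no stated format. None explicitly requests the location found, no comparator is named, and none of the five named analyses compares two location readings. One of three secondary objectives is therefore left without a planned answer. The primary objective, migration, is not affected.

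This rests on the Section 8.1 list being a fair guide to the data collection form. A location field on the form would supply part of what is missing, but not the comparator or the comparison. This is a cheap improvement, and more than a matter of wording, because it changes what is collected or what may be concluded.

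**What to change.** 1. Keep the yes/no items and add two abstracted fields: the location documented by the verifiers at insertion, and the tip location in the x-ray report where an x-ray was already taken. No new procedure or x-ray is needed.
2. In Section 8, name the main comparison: percent agreement between the verifiers' location and the x-ray location, classified by the study's zones, with an exact 95% CI. State beforehand how report wording maps to zones. Report it for the selected subset with an x-ray, and call it independent only if x-ray is not itself part of dual verification.
3. Report agreement between the verifiers' location and the two-reader zone of the insertion tracing as reader agreement only, not as validation, because the bedside process may rest on the same tracing (an assumption; the available text does not say).
4. If the results are not in the record, reword objective 3 to describe how often dual verification is performed, which the yes/no item can answer.

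The cost is modest extra record abstraction, a short analysis paragraph and a narrower conclusion. The rewording in step 4 needs no new data.
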